## **6. TREATMENT OF PATIENTS**

### **6.1 Patient Enrollment**

Before any study related assessments, all potential patients will provide written informed consent. After written informed consent has been obtained and eligibility has been established, the study site will obtain the patient's identification number and treatment assignment from the Interactive Response Technology System. Once a patient identification number has been assigned, it will be used to identify the patient throughout the study, and it cannot be reassigned to another patient.

[figure not shown]
Investigational sites will provide the Medical Monitor with a completed Eligibility Checklist and relevant redacted source documents for medical history and concomitant medications for Sponsor review. Patients who meet the eligibility criteria may be enrolled. Patients will be considered enrolled upon randomization.

Patients who cannot complete the procedures within the Screening window or are not initially eligible may be rescreened. In this situation, a new patient identification number will be assigned. For rescreening within the original Screening window, certain Screening procedures may not need to be repeated. Reconsent is required for rescreening outside the original Screening window.

[figure not shown]
An investigational drug accountability log must be used for drug accountability. For additional details on investigational study drug management, please refer to the Pharmacy Manual. Patients will be provided with a patient diary to record study product administration and compliance.

[figure not shown]
## 6.2 Milademetan Administration

[figure not shown]
Milademetan 260 mg QD will administered orally on Days 1 to 3 and Days 15 to 17 of each 28-day cycle. Milademetan will be administered at the clinical site on the indicated visit days (Cycle 1: Days 1, 3, and 15, Cycles 2 and 3: Days 1 and 15, and Cycles 4+: Day 1 only; [Table 1](#))

### 6.2.1 Milademetan Dose Modifications

## **6.3 Trabectedin Administration**

Trabectedin will be administered at 1.5 mg/m^2 BSA as a 24-hour IV infusion, every 3 weeks through a central venous line. Clinical laboratory assessments must be resulted and evaluated prior to administration of study drug on the day of administration.

### **6.3.1 Trabectedin Dose Calculation**

The dose administered will be based on the patient's BSA determined on Day 1 ( $\pm$  7 days) of each cycle. The DuBois and DuBois formula for BSA calculation is:

$$\text{BSA} = (W^{0.425} \times H^{0.725}) \times 0.007184$$

[figure not shown]
Investigational sites are instructed to use the DuBois and DuBois formula but may also use the formula/method in current institutional practice if accurate dose calculation can be assured.

### **6.3.2 Trabectedin Infusion Duration**

Reconstituted, diluted trabectedin solution should be infused over a 24-hour period through a central venous line using an infusion set with a 0.2 micron polyethersulfone in-line filter to reduce the risk of exposure to adventitious pathogens that may be introduced during solution preparation.

Infusion must be completed within 30 hours of initial reconstitution. Discard any unused portion of the reconstituted product or infusion solution.

### **6.3.3 Trabectedin Dose Modifications**

#### **6.4                    Premedication**

Administer dexamethasone (or equivalent) and antiemetics per institution's standard-of-care 30 minutes before each dose of trabectedin.

#### **6.5                    Treatment Beyond Progression**

Patients with disease progression who meet the following criteria:

- a. Absence of symptoms and signs indicating clinically significant progression of disease.
- b. No decline in ECOG or Karnofsky performance status.
- c. Absence of symptomatic rapid disease progression requiring urgent medical intervention (e.g., symptomatic pleural effusion, spinal cord compression)

may continue to receive study drug if, in the opinion of the Investigator, the patient is still benefiting (e.g., asymptomatic systemic progression or local symptomatic progression) following discussion with and approval by the Medical Monitor (or designee). The Investigator should periodically discuss the ongoing treatment with study drug with the Medical Monitor. Where applicable the IRB/IEC will be notified of any planned treatment beyond progression. Patients may receive palliative radiation to disease sites of progression, including brain metastases, following discussion with and approval by the Medical Monitor (or designee).

At the time of radiographic progression of disease, patients should be informed of treatments with known clinical benefit they may be foregoing in order to continue receiving the investigational product.

#### **6.6                    Compliance**

Investigators are required to conduct the study in compliance with the protocol. Compliance with the protocol will be closely monitored. Important aspects of compliance with this clinical study include:

- Eligibility
- Study drug administration, including:
  - Dose calculation, for the trabectedin arm
  - Dose modification
  - Infusion duration, for the trabectedin arm
- Performance of protocol-specified assessments
- ECG monitoring
- AE reporting

Protocol deviations are defined as any departure from the protocol or associated instructions and will be monitored. Deviations from the protocol, including violations of inclusion/exclusion criteria, will be assessed as “minor” or “major”. Protocol deviations at investigational sites will be discussed with the Investigator and additional training will be provided as needed to secure Investigator compliance.

Study staff will receive additional training as needed to prevent noncompliance.

## **6.7 Study Visits**

[figure not shown]
Protocol-required assessments scheduled for each study visit are summarized in the Schedule of Events ([Table 1](#) [milademetan arm] and [Table 4](#) [trabectedin arm]) and described below. In exceptional circumstances with prior Sponsor approval, study visits may be performed by local provider.

### **6.7.1 Screening Period/Baseline Assessments**

Patients may be screened anytime during the 21 days prior to randomization. Unless otherwise specified, baseline assessments may be done anytime following consent and prior to randomization. Patients who are determined not to meet eligibility criteria at any time prior to randomization will not be enrolled. The following will be assessed or measured at screening/baseline:

- Informed consent
- Eligibility (including tumor assessment)
- Medical/Disease history including all anticancer treatment
- Demographics
- Physical examination and vital signs, including height and weight
- ECOG
- ECG (12-lead) in triplicate

- Collect blood samples for laboratory assessments (see [Table 2](#) [milademetan arm] and [Table 5](#) [trabectedin arm]); ensure a serum pregnancy test is collected within 21 days of Cycle 1 Day 1 for WOCBP
- Patient-reported outcome questionnaire (EORTC QLQ-C30)
- Tumor tissue
  - Formalin-fixed paraffin embedded (FFPE) block from newly obtained biopsy or archival tissue of approximately 25 FFPE sections. Two sections will be used for eligibility confirmation after enrollment (enrollment is based on local pathology). The remaining 23 sections will be used for future genetic testing.

- In patients who provide consent to the optional procedure:
  - Tumor biopsy consisting of sufficient tissue to generate an FFPE block of approximately 25 sections. Refer to the study Laboratory Manual for details.
- Concomitant medications
  - Record all concomitant medications used after 21 days prior to Cycle 1 Day 1
  - Special attention should be accorded to medications that are known to cause prolongation of QTc or deplete potassium
- Baseline physical and radiographic tumor assessment
  - Perform physical examination and radiological assessments per RECIST version 1.1; include a computed tomography (CT) scan or magnetic resonance imaging (MRI) of the chest, abdomen, and pelvis, unless otherwise clinically indicated. The baseline radiographic tumor assessment is required within 28 days ( $\pm$  1 week window [7 days]) prior to the first dose of study drug.

### 6.7.2 Treatment Period

See the Schedule of Events for the timing of procedures during the Treatment Period ([Table 1](#) [milademetan arm] and [Table 4](#) [trabectedin arm]). Blood samples will be collected at the time points indicated in [Table 2](#) (milademetan arm) and [Table 5](#) (trabectedin arm). If screening laboratory assessments were performed within 72 hours of Cycle 1 Day 1 dosing, these screening laboratory assessments can be used as Cycle 1 Day 1 safety laboratory assessments.

Physical and radiographic tumor assessments will be performed at the end of Week 8, Week 16, Week 24, and Week 32; and then every 12 weeks ( $\pm$  1 week [7 days]) until treatment discontinuation, and any other time during the study as clinically indicated. In accordance with RECIST version 1.1, response (PR and CR) must be confirmed by a subsequent tumor assessment at least 4 weeks after the initial observed response. The same imaging modality used for baseline imaging (i.e., CT or MRI) must be used for subsequent radiographic tumor

assessments. Any dose interruption after starting study treatment will not cause adjustment to the tumor assessment schedule. Additional tumor assessments may be performed as clinically indicated (e.g., if disease progression is suspected).

### **6.7.3 End-of-Treatment Visit**

The EOT Visit should take place 30 days ( $\pm$  7 days) after the last study drug administration or before starting new anticancer treatment. If the patient begins another form of anticancer therapy before the end of the 30-day period, every effort will be made to complete all EOT assessments before commencing the new therapy. If there is an AE in need of monitoring beyond the EOT Visit, patients will be followed until resolution or confirmed stability of the AE. The following will be performed at the EOT Visit:

- Collect blood samples for laboratory assessments (see [Table 2](#) [milademetan arm] and [Table 5](#) [trabectedin arm])
- Urine pregnancy test in WOCBP
- ECOG
- Physical examination and vital signs, including height and weight
- Record AEs
- Record concomitant medications
- Patient-reported outcomes questionnaire (EORTC QLQ-C30)
- In patients who provide consent to these optional procedures: tumor biopsy consisting of sufficient tissue to generate an FFPE block of approximately 25 sections. Refer to the study Laboratory Manual for details.

### **6.7.4 Long-Term Follow-Up**

Once a patient has completed the EOT Visit, they will enter the follow-up phase. All patients will be followed for documentation of disease progression and survival information (i.e., date and cause of death) and subsequent treatment information (i.e., date/duration of treatment, response, and subsequent disease progression). Long-term follow-up will continue every 12 weeks ( $\pm$  7 days) until the endpoint of death, the patient is lost to follow-up, or for 24 months following the first dose of study drug of the last patient enrolled, whichever comes first.

[figure not shown]
## **6.8 Concomitant Medications and Treatments**

All concomitant medications (prescription and over-the-counter) and blood products taken from the Screening Visit until the EOT Visit will be recorded. The reason(s) for treatment, dose, and dates of treatment will be recorded. In addition, concomitant medications used to treat AEs occurring up to 30 days after the last dose of study drug will be recorded.

See [Appendix A](#) for a list of prohibited medications and those medications that are permitted but should be used with caution during the study. Supportive care should be provided as appropriate

to each patient to manage disease-related symptoms (e.g., antiemetics, antibiotics, transfusions, nutritional support, and pain control) according to institutional guidelines.

#### **6.8.1 Prohibited Medications**

## 7. ASSESSMENT OF EFFICACY

Tumor assessments via imaging (CT scans or MRIs) will be performed by both the Investigator and a blinded central review committee; the evaluation of tumor response will be based on RECIST version 1.1. The primary efficacy objective is to compare PFS, as determined by BICR, between patients receiving milademetan versus trabectedin. However, the decision to discontinue study drug for disease progression will be determined locally by the Investigator.

Tumor response evaluations will be performed at screening; at the end of Week 8, Week 16, Week 24, and Week 32; and then every 12 weeks ( $\pm$  1 week [7 days]) while the patient remains on study drug, and any other time during the study as clinically indicated.

In accordance with RECIST version 1.1, response (PR and CR) must be confirmed by a subsequent tumor assessment at least 4 weeks after the initial observed response. The scheduling of subsequent tumor assessments may be adjusted based on the date of the most recent imaging. Investigators are instructed to ensure that original images (or high-quality copies) of all baseline and on-study scans are filed and available for transmission to the Sponsor (or designee) for central reading.

### 7.1 Primary Efficacy Endpoint

The primary efficacy endpoint is PFS, as determined by BICR.

### 7.2 Secondary Efficacy Endpoints

Secondary efficacy variables include:

- OS
- DCR by BICR and Investigator assessment
- ORR by BICR and Investigator assessment
- DOR by BICR and Investigator assessment
- PFS by Investigator assessment
- HRQoL evaluations:
  - EORTC QLQ-C30

## 8. ASSESSMENT OF SAFETY AND EXPLORATORY VARIABLES

### 8.1 Definitions

#### 8.1.1 Adverse Event Definitions

An AE is any untoward medical occurrence associated with the use of a drug in humans, whether or not considered drug-related. An AE can be any unfavorable and unintended sign (e.g., an abnormal laboratory finding), symptom, or disease temporally associated with the use of a drug and does not imply any judgment about causality. An AE can arise with any use of the drug (e.g., use in combination with another drug) and with any route of administration, formulation, or dose, including an overdose.

### **8.1.1.1 Events Not Considered to be Adverse Events**

AEs do not include the following events:

- Medical procedures, such as surgery, endoscopy, tooth extraction, or transfusion; however, the condition that led to the procedure may be an AE and must be reported
- Preexisting diseases, conditions, or laboratory abnormalities present or detected before the Screening visit that do not worsen after the initiation of study drug
- Situations where an untoward medical occurrence has not occurred (e.g., hospitalization for elective surgery or social and/or convenience admissions)
- Overdose without clinical sequelae, as overdose is a special situation that should be reported using the Special Situation Report Form
- Any medical condition or clinically significant laboratory abnormality with an onset date of on or after the informed consent form is signed but before the first dose of study drug and not related to a protocol-associated procedure. In this case, the condition or clinically significant laboratory abnormality is not an AE but should be considered preexisting and should be documented as medical history.
- An event that is part of the natural course of the disease under study (i.e., disease progression, death due to disease progression) should not be recorded as an AE or SAE; however, signs and symptoms of clinical sequelae resulting from disease progression will be reported if they fulfill the definition of AE or SAE. If there is any uncertainty as to whether an event is due to disease progression, it should be reported as an AE.

### **8.1.1.2 Serious Adverse Events**

An AE is considered “serious” if, in the view of either the Investigator or Sponsor, it results in any of the following outcomes:

- Death
- Life-threatening (immediate risk at the time of the event)
- Inpatient hospitalization or prolongation of existing hospitalization
- Persistent or significant incapacity or substantial disruption of the ability to conduct normal life functions
- Congenital anomaly/birth defect

Any other important medical event, as defined as an AE that may jeopardize the patient or require medical or surgical intervention to prevent one of the outcomes listed above, based upon appropriate medical judgement, should be reported as an SAE. Examples of such medical events include allergic bronchospasm requiring intensive treatment in an emergency room or at home, blood dyscrasias or convulsions that do not result in inpatient hospitalization, or the development of drug dependency or drug abuse.

## **8.2 Adverse Events Reporting**

### **8.2.1 Adverse Event Collection Period**

After signing the informed consent, but before the initiation of study drug, an event must be collected and entered on the AE case report form (CRF), **IF** it is related to protocol-required procedures (e.g., biopsy); otherwise, the event must be reported as medical history.

Following initiation of study drug, all AEs, regardless of causality, will be collected and entered on the AE CRF until 30 days after the last administration of study drug or until initiation of another anticancer therapy, whichever comes first.

All AEs should be followed until resolution or until the AE is stable, if possible. The Sponsor may request that certain AEs be followed beyond the protocol-defined follow-up period.

### **8.2.2 Adverse Event Term**

AEs must be reported using standard medical terminology. The use of abbreviations (standard and nonstandard) should be avoided to help ensure a clear understanding of the event. An example of a standard abbreviation that may have several meanings is “MI” which could mean “myocardial infarction” or “mitral insufficiency.” All AE terms will be coded using a standardized dictionary (i.e., Medical Dictionary for Regulatory Activities [MedDRA]). Generally, when reporting a well-known and understood condition, it is preferable to report the overall diagnosis rather than the individual signs and symptoms. The term “intermittent” should be avoided as the duration and incidence of events helps in understanding the safety profile of the study drug.

### **8.2.3 Adverse Event Severity**

AEs will be reported at the highest experienced severity. AE severity will be graded according to NCI CTCAE version 5.0. A copy of the document will be provided to investigational sites and an electronic version is available at:

[https://ctep.cancer.gov/protocolDevelopment/electronic\\_applications/docs/CTCAE\\_v5\\_Quick\\_Reference\\_8.5x11.pdf](https://ctep.cancer.gov/protocolDevelopment/electronic_applications/docs/CTCAE_v5_Quick_Reference_8.5x11.pdf)

The terms “severe” and “serious” are not synonymous. Severity refers to the intensity of an adverse event (e.g., rated as mild, moderate, or severe, or according to the NCI CTCAE); the event itself may be of relatively minor medical significance (e.g., severe headache without any further findings).

Events not listed in NCI CTCAE will be graded according to the criteria described in [Table 133](#).

**Table 13: Severity Grading Guideline for Adverse Events Not Listed in NCI CTCAE**

Adverse Events Not Listed in NCI CTCAE Version 5.0	
Grade	Description
1	

• Mild

• Asymptomatic or mild symptoms

• Clinical or diagnostic observations only

• Intervention not indicated

2	

• Moderate

• Minimal, local or noninvasive intervention indicated

• Limiting age-appropriate instrumental activities of daily livinga

3	

• Severe or medically significant but not immediately life-threatening

• Hospitalization or prolongation of hospitalization indicated

• Disabling

• Limiting self-care activities of daily livingb

4	

• Life-threatening consequences

• Urgent intervention indicated

5	

• Death related to adverse event

NCI CTCAE = National Cancer Institute Common Terminology Criteria for Adverse Events

a Instrumental activities of daily living refer to preparing meals, shopping for groceries or clothes, using the telephone, managing money, etc.

b Self-care activities of daily living refer to bathing, dressing, and undressing, feeding self, using the toilet, taking medications, and not bedridden.

Note: A semicolon indicates “or” within the description of the grade.

#### **8.2.4 Adverse Event Duration**

The start date (the date that the event was first noticed) and the end date (the date that the event had completely resolved, returned to baseline, or improved in severity grade) will be recorded. If the exact date is not known, the best estimate should be reported.

#### **8.2.5 Adverse Event Causality**

Where the determination of the relationship of the AE to study drug rests on medical judgment, the determination must be made with the appropriate involvement of the Investigator, or, if the Investigator is not a physician, a designated Sub-investigator who is a physician.

Using the following criteria, Investigators will assess whether there is a reasonable possibility that the study drug caused or contributed to the AE.

#### **Related (Possibly, Probably, or Definitely Related)**

- The time sequence between the onset of the AE and study drug administration is consistent with the event being related to study drug; and/or

- There is a possible biologic mechanism for study drug causing or contributing to the AE; and the AE may or may not be attributed to concurrent/underlying illness, other drugs, or procedures.

### **Not Related (Unlikely Related)**

- Another cause of the AE is most likely; and/or
- The time sequence between the onset of the AE and study drug administration is inconsistent with a causal relationship; and/or
- A causal relationship is considered biologically unlikely.

### **8.3 Serious Adverse Events Reporting**

**Error! Reference source not found.** Investigators must report all SAEs regardless of causality immediately (within 24 hours of learning of the event without undue delay) on the AE CRF. If the EDC system is unavailable, SAEs must be reported by completing the back-up paper on the SAE report form and emailing the completed form to:

An event that results in hospitalization or prolongs an existing hospitalization will not be considered an SAE, if the only reason for that hospitalization or prolongation is:

- To administer study drug
- To conduct protocol-specified study procedures
- For placement of permanent IV catheter
- Hospice placement due to PD
- Respite care

**Table 14: Severity Grading Guideline for Infusion-Related Reactions**

Grade	Infusion-Related Reactions	Description
1	

• Mild transient reaction;

• Infusion interruption not indicated;

• Intervention not indicated

	
2	

• Therapy or infusion interruption indicated but responds promptly to symptomatic treatment (e.g., antihistamines, nonsteroidal anti-inflammatory drugs, narcotics, and intravenous fluids);

• Prophylactic medications indicated for <math>\leq 24</math> hours

	
3	

• Prolonged (e.g., not rapidly responsive to symptomatic medication and/or brief interruption of infusion);

• Recurrence of symptoms following initial improvement;

• Hospitalization indicated for clinical sequelae

	
4	

• Life-threatening consequences;

• Urgent intervention indicated

	
5	

• Death

	

Adapted from National Cancer Institute Common Terminology Criteria for Adverse Events v5.0

Note: A semicolon indicates “or” within the description of the grade.

## **8.5 Reporting Disease Progression and Death**

PD, also referred to as disease progression, and death due to any cause are study endpoints and information related to these events will be collected in eCRFs specifically designed to collect these data. These events will not be reported as AE/SAEs unless the Investigator feels that they are accelerated, atypical, or related to study drug. All deaths must be communicated as soon as possible to the appropriate IRB/IEC and/or reported in accordance with local laws and regulations.

If an autopsy is performed, a copy of the report will be requested and provided to the Sponsor, if available.

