### **7.6.4. Adverse Events, Serious Adverse Events, and Deaths**

All AEs and SAEs will be reported until 30 days after the last dose of investigational product(s) and will be followed until resolution or until condition stabilizes. AEs and SAEs will be coded using the Medical Dictionary for Regulatory Activities (MedDRA) 24.1 and graded by the Investigator according to the NCI CTCAE v5.0 or later.

Summaries of adverse event will, in general, focus on TEAEs which is defined as adverse event that occurs or worsens on or after first dose of investigational product and up to 30 days after the last dose. Missing data for safety endpoints will not be imputed. If dates are missing or incomplete for adverse event therefore TEAE status cannot be determined, then this AE will be included as an TEAE in the safety analysis.

Subject incidence of the following events will be tabulated in two formats: 1) system organ class (SOC), preferred term (PT), and grade by treatment group; 2) PT only and by treatment group.

- All TEAEs
- SAEs
- Treatment-related TEAEs
- Treatment-related SAEs
- Grade 3 or 4 TEAEs
- TEAE leading to treatment discontinuation, dose reduction, dose interruption
- TEAEs with an incidence >10%
- TEAEs with at least a 5% difference in incidence rates between treatment groups

Listings of TEAEs, TEAEs leading to IP discontinuation, TEAEs related to study treatment, and SAEs will be provided. Listings will be sorted by treatment, patient ID and study day; SAEs will be flagged. All AE listings will include treatment arm, patient ID, study day, SOC, PT, reported term, dose, Cycle/day, AE onset date, AE end date, outcome, duration, relationship to drug, action taken, and severity.

The incidence of death will be summarized by cause of death, treatment arm, and on-study status at time of death (within 30 days of last dose vs. more than 30 days after last dose). Patient death listings will include all death data available including date of death, cause of death and any AEs resulting in death.

AE of special interest may be identified and summarized.

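### Protocol 8.5 keeps a death from any cause out of AE/SAE reporting unless the Investigator sees a reason to report it, in conflict with Protocol 8.1.1.1, 8.1.1.2, 8.2.1 and 8.3

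*Protocol*

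**What the plan says.** Protocol 8.5 covers two events. One is disease progression. The other is given as "death due to any cause are study endpoints and information related to these events will be collected in eCRFs" designed for that purpose. The rule that follows applies to both: "These events will not be reported as AE/SAEs unless the Investigator feels that they are accelerated, atypical, or related to study drug". The section asks for prompt notice of deaths to the ethics committee, but it sets no time limit for telling the Sponsor.

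Four other protocol sections bear on the same deaths:

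- **8.1.1.1** removes the natural course of the disease from the AE definition and spells out what that covers: "disease progression, death due to disease progression) should not be recorded as an AE or SAE" (the bracket closes the protocol's own gloss). The same bullet ends: "If there is any uncertainty as to whether an event is due to disease progression, it should be reported as an AE".
- **8.1.1.2** makes an AE serious if, "in the view of either the Investigator or Sponsor, it results in any of the following outcomes", and death heads the list of outcomes.
- **8.2.1** sends AEs to the AE CRF once study drug has started, whether or not they are thought drug-related. Collection runs to 30 days after the last dose, or to the next anticancer therapy if that is earlier.
- **8.3** says "Investigators must report all SAEs regardless of causality immediately" and allows 24 hours from learning of the event.

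SAP 7.6.4 tabulates TEAEs and SAEs by system organ class, preferred term and grade. Separately, it summarizes deaths by cause, by arm, and by whether they fell within 30 days of the last dose. It also lists all available death data, including any AE that led to death.

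**The concern.** The 8.5 exemption is wider than the one in 8.1.1.1. It takes in every death, not only deaths from progression, and it makes non-reporting the default where 8.1.1.1 makes reporting the default in case of doubt. What brings a death back into AE/SAE reporting under 8.5 is the Investigator's view that it was accelerated, atypical or drug-related. The trial is open-label, so that view is formed with knowledge of the arm.

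The title of 8.5 names death, so it is a natural place for a site to look when a patient dies. In the visible text, the 24-hour clock runs only through the SAE route, and 8.5 closes that route by default. At stake are the completeness of expedited reporting and the fatal rows of the TEAE and SAE tables. SAEs are a stated safety endpoint, and the IDMC reviews unblinded safety data.

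**Working it through.** The point rests on no sample size, power or event count, and the plan gives no figure to reproduce. The check sets the rules side by side.

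**Step 1. What 8.5 exempts.** The phrase opening the exemption refers back to the two events just named, and the second is qualified only by "death due to any cause are study endpoints". Nothing in 8.5 narrows it to death from progression.

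**Step 2. Apply both sets of rules to three deaths inside the 8.2.1 collection window.**

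| Death | Under 8.1.1.1, 8.1.1.2, 8.2.1 and 8.3 | Under 8.5 read literally | Conflict? |
|---|---|---|---|
| (a) Typical death from progression | Not an AE/SAE | Not an AE/SAE | No |
| (b) Death from another cause, such as infection, judged unrelated to drug and neither accelerated nor atypical | SAE, reported within 24 hours regardless of causality | Not reported as an AE/SAE | Yes |
| (c) Death that may or may not be due to progression | Reported as an AE; with death as the outcome it is serious | Not reported unless one of the three triggers is judged to apply | Yes, the defaults are opposite |

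**Step 3. Trace each death to the outputs.** All three go onto the dedicated eCRFs, so all three count for OS and total deaths and enter the SAP 7.6.4 death summary and listing. Only in (b) and (c) can the two rule sets give different results. The outputs affected are the expedited SAE report, the fatal-grade rows of the TEAE and SAE tables, and the field for AEs resulting in death in the death listing.

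**Step 4. Bound the affected set.** It consists of deaths that fall in the AE collection window, are not clearly due to progression, and are not judged accelerated, atypical or drug-related. The documents give no rate for such deaths in either arm.

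**The case against.** The strongest reply is that 8.5 may mean only that death itself is not an AE term. On that reading a fatal infection, bleed or cardiac event is still an AE, goes onto the AE CRF under 8.2.1, becomes serious under 8.1.1.2 because of its outcome, and is reported under 8.3. Protocol 8.2.2 supports this by preferring the diagnosis as the AE term. The reading is reasonable, and it means a site following 8.5 would not necessarily lose such an event. But 8.5 does not say this, and the reading gives no help where no underlying event has been identified.

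Several stronger inferences are tempting, and the documents do not support them:

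- **That deaths go uncounted.** They do not. The death eCRFs and the SAP 7.6.4 death summary carry no AE or causality filter.
- **That an unexplained sudden death could never reach SAE reporting.** This is too absolute. The uncertainty rule in 8.1.1.1 points to reporting, and the Investigator could well call such a death atypical under 8.5.
- **That the filter is purely a causality judgement.** Two of the three triggers are not about causality, and 8.1.1.2 lets the Sponsor judge seriousness too.
- **That the SAP loses fatal events again through its "Grade 3 or 4 TEAEs" table.** A fatal event is Grade 5 and so is absent from that table. It still appears in the all-TEAE and SAE tables by grade, and the death is in the death summary. That table is a presentation choice and needs no change on this account.
- **That safety signals would reach the IDMC late.** The charter is not available, and SAP section 6 has the IDMC reviewing accumulating data.

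Section 8.4 is redacted and may add reporting rules. It would not remove the conflict among the sections that can be read.

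**Conclusion.** The point holds as an inconsistency in the reporting rules. Protocol 8.5 conflicts with 8.1.1.1 in both scope and default, and with 8.1.1.2, 8.2.1 and 8.3 taken together. It matters for deaths in the AE collection window that are not clearly due to progression. For these, a site that follows 8.5 literally could omit the expedited report and the fatal TEAE/SAE entry. OS, total deaths and the SAP death summary and listing are sound. The conclusion assumes that some sites will read 8.5 as written and not as a rule about AE terms alone.

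The size cannot be estimated. With about 160 patients randomized 1:1 there are about 160 / 2 = 80 per arm, so one omitted fatal event changes an arm's rate by about 1 / 80 = 1.25 percentage points. The documents do not say how many such deaths to expect or what share would be judged unreportable. A reader might also infer a bias between arms. An open-label judgement makes that possible, but nothing in the documents shows its direction or size.

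**What to change.** Reconcile 8.5 with 8.1.1.1 and 8.3:

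1. In 8.5, limit the exemption from AE/SAE reporting to progression and to death due to progression of the disease under study.
2. State that any other death in the AE collection period, including an unexplained death, is reported under 8.3 regardless of causality.
3. Keep all deaths, whatever the cause, as endpoint events on the dedicated eCRFs, so that OS and PFS ascertainment does not change.

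No SAP table needs to change. The cost is a short protocol wording change and a memo to sites. The downside is small: a few more expedited reports.
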